Official Title:	A Pilot Randomized Trial of Video-based Family Therapy for Depressed Home Visited Mothers
NCT number:	NCT04741776
Document Type:	Protocol and Statistical Analysis Plan
Date of the Document:	10/08/2020

Study Protocol

Study Purpose: Assess the feasibility, acceptability, tolerability, safety, and preliminary effectiveness of a video-based family therapy intervention (Resilience Enhancement Skills Training, REST) in home visited mothers (pregnant and postpartum) with moderate to severe depressive symptoms and moderate to high family conflict.

Study Design: Effectiveness-implementation hybrid type 1 design with a pilot randomized trial.

Sample Size: We aimed to enroll 80 home visited mothers and their family members (N=160) in the study.

Characteristics of Subject Population: Mothers, at least 15 years old, in any trimester of pregnancy through 18 months postpartum, enrolled in participating home visiting (HV) agencies with moderate to severe depressive symptoms on the Beck Depression Inventory-Second Edition [BDI-II] scores of ≥ 20 and moderate to high family conflict with their family members on the Perceived Hostility Survey (Ages 18+) raw scores of at least 16 or Perceived Hostility Survey (Ages 8-17) raw scores of at least 14. *Family member* is defined as the mother's adult relative or her current intimate partner with whom she either lives with in the same home or has at least weekly contact. *Family* is defined as a dyad that includes the mother and her family member.

Scheme. The mother was the unit of randomization in the study. Block randomization with block size of 4 using R package “Blockrand” was used to randomize the mothers to the study groups. Mothers were randomized with equal probability to one of two study groups: 1) video-based family therapy (Resilience Enhancement Skills Training, REST), or 2) the active comparison condition standard of care (Video-delivered individual Problem Solving Therapy, V-PST). The family received REST. Although only the mother received V-PST, the mother and her family member were asked to complete outcome measures.

Process and blinding. The Statistician used Blockrand to randomize the mothers, by unique study IDs, to the study groups. The PI communicated with Statistician to obtain the study group assignments by unique study ID. The PI called the therapist and family to communicate the study group assignment on the same day the mother and her family member completed the baseline interview. The Research Assistants remained blind to study group assignment, and study participants (mothers and their family members) were instructed by the PI not to discuss their study group assignment with the Research Assistant who administered the study questionnaires to them. In addition, the PI instructed the Research Assistants to remind each study participant not to disclose the study group assignment prior to administering each study questionnaire. Research assistants were regularly supervised by the PI.

Outcomes: The primary outcomes included maternal depressive symptoms (measured using the Beck Depression Inventory-Second Edition), family conflict (measured using the Perceived Hostility Survey Ages 18+ and Ages 8-17 years old), and family cohesion (measured using the Multidimensional Scale of Perceived Social Support – Family subscale). The secondary outcome included maternal job attainment/school enrollment measured using an adapted ABCD study item. Outcomes were assessed from baseline through post-intervention (within one week of the final therapy session), three months later, and six months later.

Monitoring Trial Performance. The PI developed and utilized structured processes for ensuring intervention fidelity and fidelity to the study protocol. For this study, the PI 1) developed initial trainings and refresher trainings for data collection procedures and adherence to safety protocols for research staff; 2) supervised the research staff to ensure adherence to recruitment, data collection, and retention procedures; 3) held weekly meetings with lead staff at participating home visiting agencies to discuss recruitment, home visitor study responsibilities, and any issues related to reallocation of home visitor study responsibilities due to home visitor turnover. In addition, the study included data entry software that minimized missing data by flagging missed items before questionnaires were submitted. The secure, password protected database was regularly maintained and monitored throughout the study.

Fidelity monitoring for the interventions occurred in two phases. In phase one, the PI and Problem Solving Therapy (PST) expert assessed fidelity on a weekly basis in all 10 audio-recorded sessions for the first 2 families who are assigned to each REST therapist. They continued to assess fidelity on a weekly basis in all 10 audio-recorded sessions for the first two mothers who were assigned to each V-PST therapist. The PI and PST expert discussed and resolved any discrepancies in these fidelity assessments. The PI immediately provided any corrective feedback to REST therapists in weekly supervision. For the V-PST therapists, the PI immediately communicated any corrective feedback to the V-PST supervisor to address with the therapists in weekly supervision.

In phase two, the PST expert assessed fidelity in 10% of randomly selected audio-recorded REST sessions, originally assessed by the PI, and 10% of randomly selected audio-recorded V-PST sessions, originally assessed by the PI. The PST expert and the PI discussed and resolved any discrepancies in the fidelity assessments throughout Years 1 and 2 of the proposed study. These fidelity assessments occurred on an ongoing basis in order to provide immediate corrective feedback to REST therapists and V-PST therapists to ensure high fidelity.

Data and Safety Monitoring Board Procedures (DSMB). The DSMB has established procedures of operation and guidelines for determining the methods and frequency for review of Departmental studies. Table 1, below, guides the risk assessment for the study. Based on the DSMB's established guidelines, the study's total score of 6 on the 10-point scoring system indicates that it poses greater than minimal risk to human subjects. Tasks related to participant safety included the PI's assessment of potential risks associated with study recruitment and participation, and the design and implementation of procedures to minimize these risks should they arise. According to the Departmental DSMB policy, studies in this risk category will be independently monitored by a group of knowledgeable faculty members and an independent statistician. The DSMB met twice per year to monitor the study, which included data analysis by the independent statistician.

Table 1. Study Risk Assessment *					ENTE R SCOR E
I. Experimental Treatment					
Low Risk	No experimental treatment in study	1 point			
Moderate Risk	Treatment effects documented from studies with similar and/or	2 points			2

	different populations and/or settings. No serious adverse events expected. Specific plans to monitor adverse events (AE's) detailed in DSM plan.			
High Risk	Experimental treatment is being regulated by the FDA (e.g., investigational drug, device, or biologic)	4 points		
II. Procedures, Measurement, and Data Collection Methods				
Low Risk	Minimally invasive with low degree of emotional and/or physical discomfort. Probability of adverse events is low. Severity (magnitude) of adverse events is low. (Procedure may be rated as low if probability of AE is moderate to high as long as the severity is low, as in the case of a bruise from phlebotomy.) Procedures that meet IRB criteria for expedited review are commonly rated as low.	1 point		
Moderate Risk	Moderate degree of emotional and/or physical discomfort. Probability of adverse events is low. Severity of adverse events is moderate to high (e.g., PET scan, lumbar puncture, arterial lines).	2 points		2
High Risk	Moderate to high degree of emotional and/or physical discomfort. Probability of adverse events is moderate to high. Severity of adverse events is high (e.g., heart muscle biopsy, insulin infusion).	4 points		
III. Decision-Making Capability				
Non-vulnerable	Adult who (1) demonstrates decision-making capacity and (2) demonstrates no perception of undue influence or coercion to participate.	1 point		

Vulnerable	Any minor. Adult who (1) demonstrates limitations in decision-making capacity and/or (2) is prone to perception of undue influence or coercion to participate.	2 points	Minors ages 15-17 years old	2
		TOTAL	6	

*Adapted with permission from Slimmer et al., Western Journal of Nursing Research, 2004, 26(7), 797-803. [170]

Details on the family recruitment procedures, consent procedures, safety monitoring procedures, and the results on feasibility, acceptability, safety and tolerability have been published (please see Cluxton-Keller F, Hegel MT. A video-delivered family therapeutic intervention for perinatal women with clinically significant depressive symptoms and family conflict: Indicators of feasibility and acceptability. JMIR Form Res. 2022;6(10):e41697. doi: 10.2196/41697. PMID: 36194458; and Cluxton-Keller F, Hegel MT, Donnelly CL, Bruce ML. Video-delivered family therapy for perinatal women with depressive symptoms and family conflict: Feasibility, acceptability, safety, and tolerability results from a pilot randomized trial. JMIR Form Res. 2023;7:e51824. doi: 10.2196/51824. PMID: 37921846).

Statistical Analysis Plan

Generalized linear mixed-effects models (GLMM) were used to analyze changes in mothers and family members, separately, with fixed effects for time (baseline, post-intervention, three-month, six-month follow-up), study group (Resilience Enhancement Skills Training, Standard of Care), and study group*time interaction. An intervention effect is indicated by a significant study group*time interaction with greater improvement in the Resilience Enhancement Skills Training group. Individual-level random intercept and slope terms were included to account for correlations from repeated measures. Significance of change from baseline to the six month follow-up was tested for mothers and family members, separately. GLMM was used that accommodates intermittent missing data and attrition, and estimate is not biased assuming missing data mechanism is missing at random (MAR) [1]. The distinction between MAR and missing not at random is not verifiable using observed data [2]. However, we did not empirically observe systematic patterns of missing in the data for this study. While MAR is a plausible assumption in many cases, minor departures from MAR typically do not invalidate the results of an MAR-based analysis. [3-4].

References

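### Perinatal stage at entry is used in neither the described randomisation nor the mothers' models; adjusting for it is a cheap way to recover a modest amount of precision

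*Combined protocol and SAP*

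**What the plan says.** Eligibility (Study Protocol, Characteristics of Subject Population) covers mothers "in any trimester of pregnancy through 18 months postpartum". The target is stated as "We aimed to enroll 80 home visited mothers and their family members (N=160) in the study".

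Randomisation (Scheme) is described as "Block randomization with block size of 4 using R package" Blockrand, and "Mothers were randomized with equal probability to one of two study groups". Neither that paragraph nor Process and blinding names a stratification factor.

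The visit schedule (Outcomes) reads: "Outcomes were assessed from baseline through post-intervention (within one week of the final therapy session), three months later, and six months later". The primary outcomes are maternal depressive symptoms, family conflict and family cohesion. For the rest, "The secondary outcome included maternal job attainment/school enrollment measured using an adapted ABCD study item".

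The Statistical Analysis Plan fits separate mixed models to mothers and to family members. These are specified "with fixed effects for time (baseline, post-intervention, three-month, six-month follow-up), study group (Resilience Enhancement Skills Training, Standard of Care), and study group*time interaction", plus an individual random intercept and slope. A significant interaction favouring REST is the criterion for an intervention effect, and change from baseline to six months is tested. Perinatal stage, gestational age and delivery do not appear in the analysis.

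**The concern.** A mother who enters in pregnancy will usually give birth between baseline and the last visit. One who enters postpartum will not have that birth during follow-up. Job or school status, and plausibly depressive symptoms and family conflict, may therefore follow different courses by stage at entry, whichever therapy is given. The model fits one mean time course per arm to both kinds of mother.

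The key contrast is a difference in change over time, so a baseline factor that predicts change adds directly to its residual variation. The random slope does not remove this. It places person-to-person linear differences in the variance, where they remain part of the uncertainty of the arm contrast. With about 40 mothers per arm and preliminary effectiveness among the stated purposes, precision is scarce. Stage is an eligibility criterion, so at least pregnant versus postpartum should be known for every mother.

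**Working it through.** **Plan's own figure.** No alpha, power, effect size, SD or dropout rate is given, so the target of 80 mothers cannot be reproduced. Only 80 × 2 = 160 can be checked, and it agrees. Equal allocation gives 40 mothers per arm.

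**Timeline.** There are 10 sessions. Their frequency is not stated outright. Weekly is inferred from the fidelity procedure, where assessors "assessed fidelity on a weekly basis in all 10 audio-recorded sessions". A 40-week term is assumed.
- Weekly sessions: 10 + 26 = 36 weeks from baseline to the six-month visit, or 37 with the one-week window. Mothers enrolled after about 40 − 36 = 4 weeks' gestation have delivered.
- Twice weekly: 5 + 26 = 31 weeks (32 with the window); cut-off about 40 − 31 = 9 weeks' gestation.
- Every two weeks: 20 + 26 = 46 weeks (47 with the window); all have delivered.
- Six months counted from baseline, which is not how Outcomes reads: 26 weeks; cut-off about 14 weeks' gestation.
- With weekly sessions, delivery precedes the post-intervention visit for mothers enrolled after about 40 − 10 = 30 weeks, and the three-month visit for those enrolled after about 40 − 23 = 17 weeks.

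**Chance imbalance.** With 40 of 80 mothers pregnant at entry (assumed), the hypergeometric distribution gives an SD of 11.3 points for the arm difference in share pregnant. The probability of a gap of at least 10 points is 50%, and of at least 20 points 12%. With 16 of 80 pregnant, the figures are 9.0 points, 40% and 5%.

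**Continuous outcomes.** Let p be the share pregnant and g the stage difference in change, in within-stage SDs. The unadjusted SD is √(1 + p(1 − p)g²) and the standard error is that SD × √(2/40). Assume a true effect of 0.6 SD and two-sided alpha of 0.05. Example: p = 0.5 and g = 1 give SD = √1.25 = 1.118 and SE = 0.250.

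| g | Unadjusted power, p = 0.5 | Unadjusted power, p = 0.2 | Adjusted power |
|---|---|---|---|
| 0.25 | 0.759 | 0.761 | 0.765 |
| 0.5 | 0.740 | 0.749 | 0.765 |
| 0.75 | 0.710 | 0.729 | 0.765 |
| 1.0 | 0.670 | 0.702 | 0.765 |

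These normal-approximation figures charge nothing for estimating the stage term. Once that is charged, the gain is about 0-2 points for g up to 0.5 and about 10 points at g = 1 with half pregnant; about 1 point is lost if g = 0. For BDI-II, an assumed stage difference of 3 to 5 points with SD 10 is 0.25 × 0.09/(1 + 0.25 × 0.09) = 2% to 0.25 × 0.25/(1 + 0.25 × 0.25) = 6% of variance.

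**Type I error.** In 20,000 simulated trials with blocks of 4, half pregnant and g = 1, the unadjusted test rejected in 4.7%.

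**Job/school status.** Simulated at six months with 40 per arm, half pregnant, odds ratio 3 and a robust linear probability model (all assumed). Power without and with a pregnant/postpartum term:
- every mother enrolled pregnant at the low rate, 10% versus 40%: 50% to 56%;
- the same with 15% versus 50%: 55% to 60%;
- the same with the extreme 10% versus 60%: 40% to 51%;
- 10% versus 40% with only 20% pregnant: 61% to 63%;
- low rate (10% versus 40%) only within 3 months after delivery: 63% to 62%;
- low rate only within 6 months after delivery: 54% to 56%.

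A change-from-baseline contrast is closer to the plan's test. With baseline rates of 10-30% independent of follow-up (assumed), and 10% versus 40% at six months, the gains are 37% to 42%, 33% to 35% and 29% to 31%.

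**The case against.** The strongest case against is that nothing here is invalid. Randomisation balances stage in expectation and the unadjusted test keeps its level. That stands.

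A reader might infer that births during follow-up bias the arm comparison, or that chance imbalance in stage is a harm on top of the noise. The documents support neither. A 20-point imbalance shifts the contrast by 0.05 to 0.20 SD for stage differences of 0.25 to 1.0 SD. That possibility is already counted in the standard error of about 0.22 to 0.25 SD. Imbalance and noise are the same loss.

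A reader might also infer that leaving stage out inflates the standard error for job/school status. On the log-odds scale, the usual one for a binary mixed model, the reverse happens. In logistic fits with the 10%/40% inputs, adding stage raised the median standard error of the arm log-odds ratio from 0.49 to 0.55 and changed the estimand to a stage-conditional one. That stands too.

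Two practical objections also hold. A pregnant/postpartum indicator is a blunt proxy for closeness to delivery. With weekly sessions, a mother enrolled at 8 weeks' gestation is about 4 weeks past her due date at the six-month visit, and one enrolled at 36 weeks is about 32 weeks past it; the indicator treats them alike. And the binary outcome is sparse: at a 10% rate, about 20 pregnant V-PST mothers yield 2 events, with probability 0.9²⁰ = 12% of none. Adding stage and three stage*time terms to a binary model that already has a random intercept and slope is not free.

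The objection does not remove the case for prespecified adjustment of the continuous outcomes by a variable that defines eligibility and plausibly predicts change. Pilot status limits the severity but does not make precision irrelevant.

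**Conclusion.** The point holds as a possible loss of precision only. Stage at entry varies widely, most mothers enrolled pregnant deliver during follow-up, and neither the described randomisation nor the model uses stage. The share pregnant, the stage differences, the job/school rates and the SDs are all assumed, because the documents give none of them.

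On those assumptions the gain from adjustment is small for continuous outcomes unless the stage difference approaches 1 SD. With half the mothers pregnant it is then about 10 power points; with 20% pregnant it is nearer 6 (0.702 to 0.765). For job/school status it is between nothing and about 6 points under most rates tried. It reached 11 only when every mother enrolled pregnant was given a 10% rate against 60%.

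The timeline conclusion rests on weekly or slower sessions and nearly holds for twice weekly. This is a cheap improvement of low severity, to be considered; it does not undermine the trial's comparison.

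**What to change.** **Primary outcomes.** In the mothers' models for BDI-II, conflict and cohesion, add baseline perinatal stage and stage*time as fixed effects, and keep study group*time as the test. Weeks from expected or actual delivery at entry is preferable, with its functional form fixed in advance, because it fits the mechanism better. If those dates were not recorded (the documents do not say), use pregnant versus postpartum.

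**Job/school status.** Use a reduced form as a sensitivity analysis, for example a risk difference at six months adjusted for stage.

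**Reporting.** Show stage at entry by arm. The SAP is written in the past tense; if the models have already been run, label the adjusted analyses as sensitivity analyses.

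**Cost.** A few degrees of freedom: with a binary stage term, four (one main effect and three interaction terms). About one power point is lost if stage is not prognostic. If a logistic model is used, the odds ratio becomes conditional on stage, and the SAP should say so.

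### Do three unranked primary outcomes, with no stated alpha or multiplicity rule, require a change to the analysis plan?

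*Combined protocol and SAP*

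**What the plan says.** The Outcomes paragraph lists the primary outcomes in one sentence: "The primary outcomes included maternal depressive symptoms (measured using the Beck Depression Inventory-Second Edition), family conflict", followed by "family cohesion (measured using the Multidimensional Scale of Perceived Social Support – Family subscale". It gives no order of importance.

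The Statistical Analysis Plan fits mixed models to mothers and family members separately, with "fixed effects for time (baseline, post-intervention, three-month, six-month follow-up", study group, and their interaction. Its criterion for success is: "An intervention effect is indicated by a significant study group*time interaction with greater improvement in the Resilience Enhancement Skills Training group". It then adds: "Significance of change from baseline to the six month follow-up was tested for mothers and family members, separately".

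The plan states no significance level or sidedness and does not say whether tests are adjusted. It has no rule for combining the three outcomes, and it names no follow-up at which greater improvement is judged. Study Purpose sets the level of ambition: the trial assesses, among other things, the "preliminary effectiveness of a video-based family therapy intervention". Study Design describes a pilot randomized trial.

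**The concern.** Three primary outcomes with a significance-based rule give three chances of a false positive. If one significant interaction were enough to say that REST works, the error rate for that statement would exceed the rate for one test. The six-month sentence looks like a second route for each outcome, because its role is not described. The four time points leave the direction of a multi-degree-of-freedom interaction open to interpretation. The cautious word, preliminary, stands in Study Purpose and not beside the decision rule. At stake is whether a chance result on one of three scales could be presented as evidence of effectiveness.

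**Working it through.** **Plan's own figure.** There is none to reproduce. The documents give no alpha, power or familywise error rate, and the target of 80 mothers has no calculation behind it.

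**Inputs.** From the documents: three primary outcomes, two groups with equal allocation, and four time points, hence a 3-df interaction if time is categorical. Assumed: two-sided 0.05 per test, all null hypotheses true, maternal outcomes only, equal correlation r between outcomes (range 0 to 0.9), and correlation 0.5 between the changes from baseline at the three follow-ups.

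**One test.** Half of 0.05 falls in each direction, so a false finding for REST has probability 0.025.

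**Three independent tests.** For REST: 1 − (1 − 0.025)³ = 1 − 0.9269 = 0.0731. In either direction: 1 − 0.95³ = 0.1426.

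**Correlated outcomes.** Row 1 comes from integrating over a shared factor. The others come from 1,000,000 simulated draws, with the interaction significant when its chi-square exceeds 7.815. Entries are the chance of at least one false finding for REST among three outcomes.

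| Rule for each outcome | r = 0 | 0.5 | 0.7 | 0.8 | 0.9 |
|---|---|---|---|---|---|
| One contrast | 7.3% | 6.3% | 5.5% | 4.9% | 4.2% |
| 3-df interaction, direction at six months | 7.3% | 6.6% | 5.8% | 5.2% | 4.4% |
| 3-df interaction, direction at any follow-up | 10.8% | 9.8% | 8.6% | 7.8% | 6.6% |
| Interaction (direction at six months) or six-month group contrast | 11.7% | 10.2% | 8.9% | 8.1% | 6.9% |

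With a follow-up correlation of 0.8 or autoregressive residuals (0.7), rows 2 and 4 move by less than 0.1 percentage point. At correlation 0.8, row 3 falls to 9.5-5.7%. If REST had to be better at every follow-up, the three-outcome rate would be about 2.3-4.3%. If all three outcomes had to succeed, the rate could not exceed that of one test, and at r = 0 it would be 0.025³ ≈ 0.00002.

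**Is the last row the plan's rule?** Set the two sentences of the Statistical Analysis Plan side by side. The first says what indicates an effect, and names only the interaction. The second reports significance of change within the two sets of respondents. It mentions no study group and is not said to indicate an effect. The last row needs two readings that the text does not supply: that the six-month test compares groups, and that it can stand in for the interaction. A within-group change would not compare REST with V-PST at all.

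**What would a change buy?**
- *Stating alpha and labelling the tests unadjusted and preliminary:* the 4.4-7.3% in row 2 stays exactly as it is.
- *Making the interaction the sole deciding test:* this repeats the existing criterion. Replacing the six-month p-value with a 95% confidence interval gives the same answer at 0.05.
- *Holm across three outcomes:* the false-finding rate falls to 2.5% at r = 0 and 1.5% at r = 0.9. A test with 80% power falls to about 66% if one effect is real, and to 72-75% if all three are.

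**The case for a change.** The strongest case for a change is that it costs only a few sentences. The decision rule carries no qualification of its own, and a pilot label does not tell a reader which test decides or whether one result in three suffices. If direction may be taken from any follow-up, the interaction alone gives 6.6-10.8%. Family-member analyses, left out above, would add to the count: five independent tests give 1 − 0.975⁵ = 11.9%.

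Much of this stands as description. Alpha, the any-or-all rule and the role of the six-month test are missing, and a careful report should state them. The argument fails as a case for altering the plan:
- The plan does name the deciding test, and baseline to six months is the one change it singles out, so six months is the natural place to read direction.
- The documents state no any-of-three success rule and no overall effectiveness claim. The inflated rate therefore belongs to a claim the plan does not make.
- All three outcomes are named, so a reader can count the tests and discount accordingly.
- The Statistical Analysis Plan already describes observed data ("we did not empirically observe systematic patterns of missing in the data for this study"). Rules written now could be disclosed but could not become prespecification.

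**Conclusion.** The omission is genuine, and analysts fill it sensibly by reporting each outcome at the conventional level, unadjusted, as pilot evidence. Its size is about 6.6-7.3% against 2.5% for outcome correlations of 0-0.5, and 4.4% at 0.9. This rests on an assumed two-sided 0.05, three maternal outcomes, categorical time, direction judged at six months, and a reader who accepts any one of three. The 7-12% range is conditional on readings the text does not give. It would be somewhat lower if time were modelled as linear, since the slope and the six-month contrast then nearly coincide (correlation about 0.95 with equally spaced visits).

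No change is needed. Wording alone alters no result. Formal adjustment is a trade-off that a pilot may reasonably decline, since it would give up power in a study meant to inform further work. What remains is a reporting courtesy: say that the tests are unadjusted, and what the six-month change compares.

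### The SAP's only model, a random-intercept-and-slope GLMM judged by group*time against baseline, is inefficient and often singular for the job/school secondary outcome

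*Combined protocol and SAP*

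**What the plan says.** Under Outcomes, the protocol names one secondary outcome: "The secondary outcome included maternal job attainment/school enrollment measured using an adapted ABCD study item". The visit schedule applies to it as to the scales: "Outcomes were assessed from baseline through post-intervention (within one week of the final therapy session), three months later, and six months later". So the item is taken at baseline too. Its response categories are not given. Nor does the text say whether it records current status or something new since baseline.

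The Statistical Analysis Plan is a single paragraph with a single model: "Generalized linear mixed-effects models (GLMM) were used to analyze changes in mothers and family members, separately". The fixed effects are time at four levels including baseline, study group, and their interaction. On the random part it says: "Individual-level random intercept and slope terms were included to account for correlations from repeated measures". The criterion for an effect is: "An intervention effect is indicated by a significant study group*time interaction with greater improvement in the Resilience Enhancement Skills Training group". The contrast of interest follows from: "Significance of change from baseline to the six month follow-up was tested for mothers and family members, separately".

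No distribution, link, alpha level or fallback for a singular fit is given, and no outcome is assigned a model of its own. Under Sample Size: "We aimed to enroll 80 home visited mothers and their family members (N=160) in the study". Under Scheme: "Mothers were randomized with equal probability to one of two study groups".

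**The concern.** The model suits a continuous scale measured repeatedly. A yes/no item carries much less information per visit. Four answers from a mother must support an intercept variance, a slope variance and their correlation, all estimated from about 80 mothers. A boundary (singular) fit is then common, and the SAP gives no rule for what to do when it occurs.

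The test also treats baseline as a response and contrasts six months with it. In a randomized trial the arms are expected to be equal at baseline, so subtracting baseline adds noise that adjusting for baseline would avoid. At this sample size there is little power to spare. At stake is how much the trial can say about its only secondary outcome, and whether a reader can interpret the result.

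**Working it through.** **The plan's own figures.** The only design figure is the enrollment target: 80 mothers x 2 people per dyad = 160, which agrees. No power calculation is given, so there is none to reproduce. Equal allocation gives 80 / 2 = 40 mothers per arm.

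**Assumptions (none is in the documents).** Yes/no item; logit link; two-sided 0.05. Main case: 40% in work or school at baseline; 50% (V-PST) v 68% (REST) at six months; 7% dropout per visit; random-intercept SD 2.5; slope SD 0 or 2 on the logit scale.

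**Step 1. Simulated behaviour under status coding.** Logistic mixed models, 80 mothers, four visits.

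| Simulation | Slope SD | Degenerate covariance | Power, six-month interaction | Power, simple six-month analysis |
|---|---|---|---|---|
| Main case, 800 trials | 0 | about 60% | 21% | 36% (baseline-adjusted risk difference) |
| Main case, 800 trials | 2 | 22-28% | 24% | 34% (same) |
| Main-case rates and dropout, separate run, 200 trials | 0 | about 60% | 24% | 39% (same) |
| Main-case rates and dropout, separate run, 200 trials | 2 | 30% | 21% | 28% (same) |
| 20-point gap, intercept SD 1.5-3, 0% or 20% lost by six months, 200 trials per scenario | 0-1 per visit | 17-52% | 23-32% | 35-48% (unadjusted) |

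With 200 trials the Monte Carlo SE is at most sqrt(0.5 x 0.5 / 200) = 3.5 points. In the last design, a 15-point gap gave 19% v 21% and a 30-point gap 52% v 68%. Under no effect the planned interaction test rejected in about 4%, and the baseline-adjusted risk difference in 3.5-4.6%.

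**Step 2. How much comes from contrasting with baseline.** Let SE be the standard error of the raw six-month difference and r the baseline-to-six-month correlation, with roughly equal variances.

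- Adjusted for baseline: SE x sqrt(1 - r^2)
- Change from baseline: SE x sqrt(2(1 - r))

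With 40 x 0.93^3 = 32 mothers per arm at six months, SE = sqrt((0.50 x 0.50 + 0.68 x 0.32) / 32) = 0.121. The assumed rates and intercept SD imply r of about 0.41-0.47 when slopes do not vary. Power is approximately Phi(0.18 / SE - 1.96), using the SE of each analysis:

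- r = 0.4: adjusted SE 0.111, power 37%; change SE 0.132, power 27%.
- r = 0.5: adjusted SE 0.105, power 40%; change SE 0.121, power 32%.

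A complete-case simulation of 3,000 trials with no random effects agrees: adjusted 36% / 33% and change 28% / 24% (slope SD 0 / 2). Set against the GLMM's 21% / 24%:

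- Slope SD 0: the gap is 36 - 21 = 15 points, of which 36 - 28 = 8 come from contrasting with baseline.
- Slope SD 2: the gap is 33 - 24 = 9 points, of which 33 - 24 = 9 do.

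**Step 3. How much comes from the random slope.** In the last design of Step 1, a random-intercept-only model had power of 30-38% for a 20-point gap, against 23-32% with the slope. Over all scenarios with an effect the slope cost about 4-10 points. Null rejection with the intercept alone was 6.5% of 200 trials, within Monte Carlo error of 5%.

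**Step 4. Coding as new since baseline.** Every mother is then 0 at baseline, so the baseline log-odds in each arm is log(0), minus infinity. The interaction subtracts one such term from the other. In an example dataset, fixing the baseline group coefficient at -3, 0 or +3 gave the same negative log-likelihood (137.22216), while the six-month interaction was 4.69, 1.69 and -1.31. The sum is the same each time: -3 + 4.69 = 0 + 1.69 = 3 - 1.31 = 1.69. The data fix the six-month difference but not the interaction.

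**The case against.** **The model class is legitimate.** A GLMM with a logit link can take a binary item. A reader might infer that the planned model is unfit, or leaves no valid test. Under status coding that is not supported. Most degenerate fits are boundary variances or correlations that still yield an interaction estimate, runaway values occurred in 0-7% of fits, and type I error is held. With no true slope variance a boundary estimate is expected anyway: a continuous outcome of the same size gave 54%.

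**Low power is mainly sample size.** This stands. For 40% v 60%, a simple comparison with 40 per arm has 43% power, and 80% power needs 97 per arm. But sample size does not explain the difference between analyses of the same data.

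**The loss is mostly a generic change-versus-adjustment choice.** This also stands in large part, as Step 2 shows. It changes the diagnosis, not the remedy, because the baseline value is already collected.

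**The all-zero baseline is hypothetical.** Correct. A reader might take the word attainment to mean new since baseline and conclude that the interaction is inestimable. No passage codes it so, and an item assessed at baseline fits current status better.

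**The SAP's statement on bias.** A reader might think small-sample inflation contradicts it. One simulation set did put the mean interaction log-odds ratio about 20% high (1.71 / 1.42 = 1.20). But the SAP's sentence is conditional on MAR and concerns missing data. Inflation of a logistic coefficient in a small sample is a separate matter and does not contradict it.

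**Conclusion.** The concern holds as one of efficiency and stability. For a yes/no job/school item at four visits in about 80 mothers, the planned model is singular in roughly 20-60% of fits. Its six-month interaction has about 20-25% power, where a baseline-adjusted risk difference has about 28-39%, with type I error held by both. Much of the gap is the contrast with baseline, and part is the random slope.

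The exact figures depend on assumed rates, dropout, random-effect SDs and a yes/no format. The advantage is small for a 15-point gap and larger for 20 or 30 points. In every scenario simulated with an effect, the simple six-month analysis had more power than the planned contrast, though for the smallest gap the difference was within simulation error. For one secondary outcome in a pilot this is worth correcting, but it does not undermine the trial.

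**What to change.** For this outcome only:

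- Code current work-or-school status (yes/no) at each visit, and say so.
- Make the main analysis the REST minus V-PST difference in six-month proportions, adjusted for baseline status, with a robust SE and 95% CI.
- Handle missing visits by multiple imputation using the mother's other statuses.
- If the GLMM is kept as supportive, state its link and drop the random slope.
- The SAP is written in the past tense, so label any reanalysis as post hoc.

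The cost is a few lines of text and one extra analysis of data already collected. There are two downsides. Intermediate visits inform the six-month result only through imputation, and this outcome uses a different model from the scales. The power figures above do not show what the imputation step itself adds. Power stays low whichever analysis is used, so the result should be read as an estimate with its interval.
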